## 8.5 Clinical laboratory evaluations

The following laboratory parameters are measured within the study:

- Hematology: red blood cell count, white blood cell count, differential count (lymphocytes, basophils, eosinophils, monocytes, neutrophils), platelet count, hematocrit, and hemoglobin
- Chemistry: calcium, serum electrolytes (sodium, potassium, chloride, bicarbonate), total protein, albumin, phosphate, glucose, uric acid, alkaline phosphatase, urea nitrogen, creatinine, aspartate aminotransferase, alanine aminotransferase, gamma glutamyltransferase, total bilirubin, cholesterol, triglycerides
- Urinalysis: albumin, specific gravity, ketones, glucose, pH, microscopic exam for blood cells or casts/high power field
- Endocrinology: FSH, LH, T3, T4, TSH

Markedly abnormal laboratory values are defined in appendix 13.2. Treatment-emergent markedly abnormal (TEMA) values are defined as those markedly abnormal values which occur during the Treatment Period (including unscheduled visits), ie, with a normal Baseline value.

Observed values and changes from Baseline will be summarized for the parameters of hematology, chemistry and endocrinology given above. The Last Visit and minimum and maximum post-Baseline values during the Treatment Period will also be presented in these summaries. Repeated or unscheduled laboratory assessments during the study will not be presented in the by-visit summaries, but will be considered when determining the Last Visit, minimum post-Baseline value, and maximum post-Baseline value.

The number and percentage of subjects with a TEMA value, TEMA low value, and TEMA high value will be summarized by parameter and visit. Percentages will be based on the number of subjects with a nonmissing value at the respective visit. Additionally, a list of subjects with at least 1 TEMA value will be provided including all laboratory measurements of the respective parameter of the respective subject.

Urinalysis and pregnancy test results will only be listed.

## 8.6 Vital signs, physical findings, and other observations related to safety

### 8.6.1 Vital signs, body weight, height, BMI, and head circumference

Markedly abnormal vital signs values are defined in Table 8–1.

**Table 8–1: Vital Signs Abnormality Criteria**

Parameter	Age Range	Abnormality Criteria
Pulse Rate (beats/minute)	<6m	<100, >180
	6m - <3y	<90, >150
	3y - <12y	<60, >130
	12y - <17y	≤50, ≥120
	≥17y	≤50 and a decrease from Baseline of ≥15 ≥120 and an increase from Baseline of ≥15
Systolic BP (mmHg)	<6m	<60, >100
	6m - <3y	<70, >120
	3y - <12y	<80, >140
	12y - <17y	<90, >160
	≥17y	≤90 and a decrease from Baseline of ≥20 ≥180 and an increase from Baseline of ≥20
Diastolic BP (mmHg)	<6m	<40, >65
	6m - <3y	<45, >75
	3y - <12y	≤50, ≥80
	12y - <17y	≤50, ≥105
	≥17y	≤50 and a decrease from Baseline of ≥15 ≥105 and an increase from Baseline of ≥15
Temperature	All	>101 °F (38.3 °C)
Body Weight	1 month - <17y	<3% or >97% of the normal body weight growth curve ranges  based on gender and the age of subject on date of weight assessment
	≥17y	≥10% change from Baseline (an increase or a decrease)

 source: [http://www.cdc.gov/growthcharts/html\\_charts/wtage.htm](http://www.cdc.gov/growthcharts/html_charts/wtage.htm)

BP=blood pressure, m=month, y=year.

A month is defined as 30 days; a year is defined as 365.25 days.

Observed values and changes from Baseline for vital signs (systolic BP, diastolic BP, and pulse rate) will be summarized by visit and position/time point including the Last Visit.

Changes of standing measurements versus supine measurements of systolic BP, diastolic BP, and pulse rate will also be summarized for each visit and time point including the Last Visit.

Observed values and changes from Baseline for body weight, height, BMI, and head circumference will be summarized by visit. The Last Visit will also be presented in this summary.

The number and percentage of subjects with a markedly abnormal value, markedly abnormal low value, and markedly abnormal high value will be presented by visit. Percentages will be based on the number of subjects with a nonmissing value at the respective visit. Additionally, a list of subjects with at least 1 markedly abnormal value will be provided including all vital sign measurements of the respective subject.

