**Table 8–2: Electrocardiogram Abnormality Criteria**

Parameter	Age Range	Abnormality Criteria
	6m-<3y	<90, >130
	3y-<12y	<60, >130
	>12y	<50, >120

bpm=beats per minute; m=months; ms=milliseconds; QTc=corrected QT interval; y=years.  
A month is defined as 30 days; a year is defined as 365.25 days.

Treatment-emergent ECG abnormalities are defined as values meeting the criteria given in Table 8–2 at any post-Baseline visit during the Treatment Period (including unscheduled visits) and not meeting the same criteria during Baseline.

For ECGs, baseline will be defined as the average of all pre-dose interpretable readings. For all post-baseline visits, the average of all interpretable readings at the specified visit will be used for summaries.

Observed results and changes from Baseline in ECG results will be summarized for all visits and the Last Visit.

The number and percentage of subjects with no abnormality, an abnormal but not clinically significant finding, and a clinically significant finding, will be summarized by visit, including last visit. Percentages will be relative to the number of subjects with an ECG assessment at the respective visit. Subjects are counted once at each visit based on the worst observed outcome across all abnormalities reported at that visit.

Summaries of shifts from Baseline to post-Baseline visits (including Last Visit) will also be provided based on the categories normal, abnormal, not clinically significant, and abnormal, clinically significant.

The number and percentage of subjects with treatment-emergent ECG abnormalities will be presented by visit and treatment group. Abnormalities reported at an unscheduled visit will be summarized under the scheduled visit preceding the unscheduled visit (if the abnormality was not present already at the preceding scheduled visit). Percentages will be based on the number of nonmissing values for the variable and visit. In addition, a listing including all ECG parameter values for subjects meeting any abnormality criteria will be provided.

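### Below 17 years the SAP's markedly abnormal pulse, blood pressure and weight counts ignore Baseline and are not treatment-emergent, and no table counts children with large weight loss

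*SAP*

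**What the plan says.** SAP 8.6.1, vital signs Table 8–1:

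- **Pulse, systolic and diastolic pressure, below 17 years:** absolute limits by age band only.
- **The same, from 17 years:** a limit plus a change. The low pulse limit is "≤50 and a decrease from Baseline of ≥15" and the low systolic limit is "≤90 and a decrease from Baseline of ≥20".
- **Weight, 1 month to below 17 years:** "<3% or >97% of the normal body weight growth curve", by sex and age at the assessment. I read the percentages as growth-curve percentiles, because the table cites a growth chart.
- **Weight, from 17 years:** "≥10% change from Baseline (an increase or a decrease", in either direction.

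On tabulation, the section says: "The number and percentage of subjects with a markedly abnormal value, markedly abnormal low value, and markedly abnormal high value will be presented by visit". It gives no treatment-emergent definition. Subjects with at least one flag are listed with all their vital sign measurements.

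Elsewhere, SAP 8.5 defines treatment-emergent laboratory abnormality as requiring a normal Baseline value. SAP 8.6.2 counts an ECG abnormality only when it occurs on treatment, "not meeting the same criteria during Baseline". SAP 3.2.5 bases all these criteria on age at assessment.

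**The concern.** The study enrols children from 1 month to below 18 years, so the Baseline-aware rows reach only the last year of the age range. For everyone else a flag says where the child stands against a fixed limit, not whether anything changed on lacosamide. There is no control arm to show the background rate, so a by-visit percentage that mixes pre-existing and new abnormality is hard to interpret as a safety result.

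The SAP gives no reason for treating vital signs differently, and paediatric practice within the SAP does not explain it: the ECG Table 8–2 applies change-from-Baseline criteria below 17 years (for example, QTc increases above 15%, and PR and QRS increases of 25% or more). Changes in vital signs and body weight are named safety variables in Protocol 4.1.3.

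**Working it through.** The documents state no figure on this point, so there is none to reproduce.

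**1. The age-17 boundary.** The low and high pulse limits are the same at 12 to below 17 years and from 17 years (50 or less, 120 or more). Only the older row adds a change of at least 15. A 16-year-old with pulse 50 at Baseline and 50 on treatment is flagged; a 17-year-old with the same readings is not. The diastolic limits (50 or less, 105 or more) behave the same way.

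**2. Children outside the weight limits at entry.** Protocol 6.1 sets only a 4 kg minimum for infants, so children outside the percentiles can enrol. Planned N is about 50.
- If the sample matches the reference: 3% + 3% = 6%, and 0.06 × 50 = 3 children. P(at least one) = 1 − 0.94^50 = 0.95.
- If 10% to 30% are outside (assumption; the documents give no rate): 5 to 15 of 50.

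Each is counted at every weight assessment while still outside, with no drug effect needed.

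**3. Weight losses the percentile rule flags.** Assumptions: weight-for-age is normal or lognormal with a coefficient of variation c of 12%, 15% or 20% (not in the documents); age is held fixed; children in range at entry are distributed as the reference. z(0.97) = 1.881.

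Loss needed for a median child to reach the 3rd percentile:
- Normal, 1.881c: 23%, 28%, 38%.
- Lognormal, 1 − exp(−1.881s) with s = √ln(1 + c²): 20%, 24%, 31%.

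Share of in-range children newly flagged low after a proportional loss L is [Φ(z*) − 0.03]/0.94, where
- normal: z* = [(1 − 1.881c)/(1 − L) − 1]/c
- lognormal: z* = −1.881 − ln(1 − L)/s

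Example, lognormal, c = 12%, L = 10%: s = 0.1196; z* = −1.881 + 0.1054/0.1196 = −1.000; Φ = 0.159; (0.159 − 0.03)/0.94 = 13.7%.

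| Loss | Normal, c = 12 / 15 / 20% | Lognormal, c = 12 / 15 / 20% | Left unflagged |
|---|---|---|---|
| 10% | 9.8 / 6.2 / 3.5% | 13.7 / 9.6 / 6.2% | 86–96% |
| 15% | 21.2 / 12.8 / 6.6% | 28.8 / 19.6 / 12.2% | 71–93% |
| 20% | 38.8 / 23.1 / 11.2% | 49.4 / 34.1 / 20.8% | 51–89% |

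The limits rise as a child grows during the study, so holding age fixed somewhat overstates the unflagged share, most of all in infants.

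**The case against.** A reader might infer that large on-treatment weight loss in children goes undetected, or that the criterion has no sensitivity to it. The documents do not support that. SAP 8.6.1 summarizes change from Baseline in weight by visit and at the Last Visit. SAP 3.1 requires minimum and maximum, by age group, and listings of all calculated changes. A loss that crosses the 3rd percentile is flagged. A reader might also infer that pre-existing abnormality cannot be told apart from new abnormality. The listing of flagged subjects shows all their measurements, so it can be, subject by subject.

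These points stand, but they leave gaps. No percent change in weight is specified, and within age groups as wide as 1 month to below 4 years the minimum change in kg can come from a heavier child's modest loss. A minimum is one extreme value, not a number of children. The listing of flagged subjects omits a child who loses weight inside the band and has no other flag. By-visit counts, even if shown for pre-dose visits, do not say who is newly abnormal.

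A simple treatment-emergent rule would also create errors of its own, because limits step at age bands and follow age at assessment. A child with a steady systolic pressure of 85 who turns 12 moves from a limit of below 80 to one of below 90. An infant with a steady pulse of 160 who reaches 6 months moves from above 180 to above 150. Both would look new with no change. A decrease rule for weight cannot register faltering growth without loss, which a percentile can. The fix has to meet both points.

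Finally, these are other safety variables (SAP 2.2.1.3) in a descriptive study, and no primary or secondary result depends on them.

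**Conclusion.** The point holds as a gap in how the counts are defined, not as a loss of data. Below 17 years the stated rule counts abnormality present at entry as on-study abnormality, out of line with SAP 8.5 and 8.6.2. For weight this is about 3 of 50 children if the sample matches the growth reference; 5 to 15 rests entirely on an assumed 10% to 30% entry rate. I have no figure for pulse or blood pressure.

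The markedly abnormal table would also leave unflagged most in-range children with a 10% or 15% loss, and about half or more with a 20% loss, under the assumed spread of weights. What the plan lacks is a count of those children. The change is worth making because it is cheap and the study has no control arm. It does not threaten the main conclusions.

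**What to change.** In SAP 8.6.1:

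1. Keep the current absolute counts by visit.
2. Add counts, by visit and at any time in the Treatment Period, of treatment-emergent markedly abnormal vital signs and weight: the Table 8–1 criterion is met on treatment and was not met in the same direction at Baseline.
3. For pulse and blood pressure, judge the Baseline value against the same age-band limits as the on-treatment value. In the two examples above, 85 is then already below 90 and 160 already above 150 at Baseline, so crossing a band creates no event. For weight, judge Baseline against the percentile for age at Baseline.
4. For subjects below 17 years, tabulate the number with a weight decrease of at least 10% from Baseline, alongside the percentile criterion and not replacing it. The threshold is borrowed from the SAP's own row for 17 years and over. Only decreases are counted, because growth makes gains expected. This is a descriptive analysis count, not a clinical management rule.

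Cost: SAP wording, a few extra table rows and a small programming change; no new data. The emergent count omits further worsening in subjects already abnormal at Baseline, which the retained absolute counts and listings still show.

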13.3.3 Other safety analyses

Other variables assessing safety are: ECG, measurements of laboratory parameters (hematology, clinical chemistry, urinalysis, and hormone status) and vital signs (including body weight, height and BMI), physical and neurological examination findings, assessments of Tanner stage (if applicable), Achenbach CBCL, and BRIEF-P/BRIEF.

Measurement and change from Baseline in continuous parameters (eg, vital signs and laboratory measurements) will be summarized using descriptive statistics. When analyzing

categorical data (eg, overall assessment of 12-lead ECG) the number and percentage of subjects in each category will be presented. In addition, shift tables may be used to evaluate the number and percentage of subjects having a different post-Baseline status when compared to their Baseline status.

The analysis of the Bayley-III scales data will be performed in the follow-up study, SP848.

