### **3 DATA ANALYSIS CONSIDERATIONS**

#### **3.1 General presentation of summaries and analyses**

Statistical analysis and generation of tables, figures, subject data listings, and statistical output will be performed using SAS Version 9.4 or higher. All tables and listings will use Courier New font size 9.

Descriptive statistics will be displayed to provide an overview of the study results. If not stated otherwise, all summaries will be displayed overall and by age group ( $\geq 1$  month to <4 years,  $\geq 4$  to <12 years, and  $\geq 12$  to <18 years). For categorical parameters, the number and percentage of subjects in each category will be presented. If not stated otherwise, the denominator for percentages will be based on the number of subjects in the respective population. Unless otherwise noted, all percentages will be displayed to 1 decimal place. No percentage will be displayed for zero counts, and no decimal will be presented when the percentage is 100%. For continuous parameters, descriptive statistics will include number of subjects (n), mean, standard deviation (SD), median, minimum, and maximum.

Decimal places for descriptive statistics will always apply the following rules:

- “n” will be an integer.
- Mean, SD, and median will use 1 additional decimal place compared to the original data.
- Coefficient of variance (CV[%]) will be presented with 1 decimal place.
- Minimum and maximum will have the same number of decimal places as the original value.

A complete set of data listings containing all documented data and all calculated data (eg, change from Baseline) will be generated, and will be sorted by site, subject number and visit (where applicable).

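### The under-17 weight flag in SAP 8.6.1 gives point prevalence, so it cannot show how many children newly crossed a growth limit on lacosamide, and the growth summaries carry no age or sex reference

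*SAP*

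**What the plan says.** **Weight flag.** In SAP Table 8-1 (Vital Signs Abnormality Criteria), weight from 1 month to under 17 years is markedly abnormal at "<3% or >97% of the normal body weight growth curve ranges", read for sex and for age on the day of weighing. I take these as the 3rd and 97th centiles. From 17 years the criterion is relative: a change of at least 10% from Baseline in either direction. SAP 8.6.1 then says that the "number and percentage of subjects with a markedly abnormal value, markedly abnormal low value, and markedly abnormal high value will be presented by visit", with every subject who has a value at the visit in the denominator. It plans a listing of all vital sign measurements for each flagged child, but no shift table.

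**Neighbouring rules.** SAP 8.5 defines treatment-emergent laboratory flags as "those markedly abnormal values which occur during the Treatment Period (including unscheduled visits), ie, with a normal Baseline value". SAP 8.6.2 counts an ECG abnormality as treatment-emergent only if it occurs after Baseline while "not meeting the same criteria during Baseline". Protocol 13.3.3 says that "shift tables may be used to evaluate the number and percentage of subjects having a different post-Baseline status when compared to their Baseline status".

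**Growth summaries.** SAP 8.6.1 states: "Observed values and changes from Baseline for body weight, height, BMI, and head circumference will be summarized by visit". Last Visit is shown as well. Under SAP 3.1, unless stated otherwise, "all summaries will be displayed overall and by age group". The three bands are 1 month to under 4 years, 4 to under 12, and 12 to under 18.

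**The concern.** The study has no control arm, so each child's own Baseline is the only comparator. A weight flag without a Baseline condition counts a child who was already below the 3rd centile before the first dose together with a child who fell below it during treatment. The safety question is how many children crossed a limit on lacosamide, and the planned table does not answer it.

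The second part concerns how growth is scaled. Height, BMI and head circumference have no row in Table 8-1, and the observed values and changes for all four measures are in raw units. In the youngest band an infant of a few months is averaged with a child approaching 4 years. Table 8-1 itself divides that band at 6 months and 3 years for pulse and blood pressure, and uses age- and sex-specific curves for the weight flag. The SAP therefore accepts the need for an age reference but does not apply one to these summaries.

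**Working it through.** The plan gives no figure on this point to reproduce. The check sets the rules side by side and then sizes the effect.

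**1. Rules compared**

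| Measure | Excludes cases already abnormal at Baseline? |
|---|---|
| Laboratory (SAP 8.5) | Yes |
| ECG (SAP 8.6.2) | Yes, and shift tables are planned for the overall findings |
| Weight, 17 years and over (Table 8-1) | Defined as change from Baseline |
| Weight, 1 month to under 17 (Table 8-1) | No |
| Pulse and blood pressure, under 17 (Table 8-1) | No |

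**2. Flags expected before any dose**

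Inputs: about 50 subjects (Protocol 5.1.2), and 3% + 3% = 6% of a reference population outside the limits by definition.

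- Expected flags = n × p = 50 × 0.06 = 3.0.
- Chance of at least one = 1 − 0.94^50 = 95.5%. For n = 40 the results are 2.4 and 91.6%.
- Allowing for 17-year-olds: if the 40 older subjects spread evenly over 4 to under 18 years (assumed), 40/14 = 2.9 are aged 17. About 47 are then under 17, and 47 × 0.06 = 2.8.

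**3. What a by-visit count can show**

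Count at a visit = Baseline count + entering − leaving. Three flagged at Baseline and four at Week 18 fits one entering and none leaving (3 + 1 − 0), and equally four entering and three leaving (3 + 4 − 3). Even with pre-dose visits tabulated, only the net is visible.

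Illustration with 47 children under 17, 2 new cases and none leaving. The 2 cases and the 10% and 20% Baseline shares are assumptions; the documents give no Baseline weight distribution.

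| Outside limits at Baseline | Table as planned | New cases among those not flagged at Baseline |
|---|---|---|
| 6% (2.8) | 4.8 of 47 = 10% | 2/44.2 = 4.5% |
| 10% (4.7) | 6.7 of 47 = 14% | 2/42.3 = 4.7% |
| 20% (9.4) | 11.4 of 47 = 24% | 2/37.6 = 5.3% |

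The planned figure follows the assumed Baseline share, while the new-case figure barely moves.

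**4. Follow-up length**

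Before taper, head circumference is taken at Visit 1 and Visit 9/ET, and height at Visits 1, 2 and 9/ET (Protocol Table 5-1). SAP 4.2.1 maps an early-termination value of either to Visit 9. With constant growth (assumed), a child stopping at Week 6 contributes (6 + 6)/24 = 50% of a completer's head-circumference change and 6/18 = 33% of the height change. If a share d stops at Week 6, the mean falls by d × (1 − fraction). For an assumed d of 10% to 30%, that is 5% to 15% for head circumference and 7% to 20% for height. Head circumference is measured only under 4 years, where at least 10 children are planned, so with 10 such children that d means 1 to 3 children.

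**The case against.** Much of the case on the other side stands.

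- **Labelling.** SAP 8.6.1 calls its count markedly abnormal, not treatment-emergent. A reader might infer that the table misreports emergent cases. It does not: it reports point prevalence and claims no more.
- **Protocol.** A reader might infer a departure from Protocol 13.3.3. That text only permits shift tables, so omitting one is no departure.
- **Raw change only.** A reader might infer that the growth measures get nothing else. Observed values are summarised too, in three age bands, and Baseline weight, height, BMI and head circumference are tabulated (SAP 6.1).
- **Recoverability.** SAP 3.1 plans complete listings of documented and calculated data. With about 50 subjects, new cases can be found by hand. Weight is measured at Visits 1 and 2, so the Baseline count may also appear in the by-visit table. Clinically significant physical examination findings after Visit 1 are reported as adverse events in any case (Protocol 11.7.5).
- **Dropout.** A reader might infer that early stopping would pass for slowed growth. A lower raw mean looks slow only against an expected value, and the plan has neither a control nor a norm. The figures also put every dropout at Week 6. This is a minor point.
- **A purely emergent count has its own fault.** A child already below the 3rd centile who loses more weight would drop out of it.

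The gap that remains is that no planned table separates new from pre-existing cases, and finding them by hand is a poor substitute for a simple table.

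**Conclusion.** The point holds, as a minor, optional improvement. The under-17 weight table cannot show how many children newly crossed a growth limit, although the SAP makes that separation for laboratory and ECG values. The only size that follows from the criterion itself is about 6% of reference-normal children, or about 3 of 50, flagged before any dose. The larger contrasts in the working rest on an assumed Baseline weight distribution, age spread and number of new cases.

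The growth summaries also lack an age or sex reference in broad bands, which limits what they can show without a control arm.

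A reader might infer that the trial's safety conclusions are at risk. The documents do not support that. These are other safety measures over about 18 weeks of treatment, head circumference is not on the declared variable list, and no primary or secondary result changes.

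**What to change.** **Main change, SAP 8.6.1.** Add a shift table (low, within limits, high) from Baseline to each post-Baseline visit and to Last Visit for the under-17 weight flag, preferably also for the under-17 pulse and blood pressure flags so that the section is consistent. Keep the by-visit counts. If an emergent percentage is given, its denominator should be subjects who did not meet the same criterion at Baseline. A shift table is better than a purely emergent count because children already outside the limits stay visible. State how a child who turns 17 during the study is classified, since SAP 3.2.5 applies age at assessment and the criterion changes at 17.

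**Secondary change.** Beside the raw summaries, give change in age- and sex-specific z-score, using age at measurement. Start with weight, from the growth reference that Table 8-1 already cites. Add height, BMI and head circumference once a reference is named for each. This would also show further loss in a child who starts below the 3rd centile.

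**Cost.** SAP wording, programming and extra output; the shift table uses only data already collected. Z-scores lose some precision where birth dates are partial: SAP 3.2.5 sets a missing birth day to the first of the month, which can overstate age by up to 30 days, an error the present weight flag already carries. Correction for prematurity may not be possible, because the documents do not say that gestational age is recorded for analysis. Without a control arm the results stay descriptive and cannot be attributed to lacosamide.
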